6.9 Duration of Follow Up

Patients will be followed as outlined in study calendar in section 7 after removal from study or until death, whichever occurs first. Patients removed from study for unacceptable adverse event(s) will be followed until resolution or stabilization of the adverse event.

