| Urinalysis | X | | | | | X | | | X | | | X | | | |
| T3, FT4 and TSH | X | | | | X | | | X | | | X | X | X | X | |
| ECG | X | | | | | | | | | | | | | | |

| Trial Period: | Main Study Screening (Visit 2) | Treatment Cycles ^a | | | | | | | | | | End of Treatment | Post-Treatment | | |
|---|--------------------------------|-------------------------------|-----|----------------|----------------|----------------|----------------|----------------|---------|----------------|--------------------------------|---------------------|---------------------------|-------------------------------|--------------------|
| | | 1 ^a | | 2 | 3 | 4 | 5 | 6 | 7 | 8 | To be repeated beyond 8 cycles | | Safety Follow-up | Follow Up Visits ^b | Survival Follow-Up |
| Treatment Cycle/Title: | 1 ^a | D-14 | D-7 | D1 | D15 | | | | | | | Discon | | | |
| Day | | | | | | | | | | | | | | | |
| Scheduling Window (Days): | -28 to -1 | | | ± 3 | $\pm 3^*$ | ± 3 | ± 3 | ± 3 | ± 3 | ± 3 | At time of Discon | 30 days post discon | Every 8 weeks post discon | Every 12 weeks | |
| Tumor Imaging | X | | | | | X ^g | | X ^g | | X ^g | | | | | |
| Newly Obtained Tissue Collection ^h | X | | | X ^h | X ^h | | | | | | | | | | |
| Correlative Studies Blood Collection ⁱ | X | | | X ⁱ | X ⁱ | | X ⁱ | | | | | X ⁱ | | | |

- a. Each cycle is 4 weeks, and there is 14 days lead in period in cycle 1
- b. Only for patients with ongoing treatment related toxicities
- c. Metformin will be taken 500 mg po BID for D-14 to-12, 500 mg am and 1000 mg pm for D-11 to 8, 1000 mg am and 1000 mg pm for D- 7 to -1, and continued 1000 mg BID for the rest of the study (if not able to tolerate 1000 mg BID during D1-14 period subject will be on maximum tolerated dose). Study coordinator will call the patient on Day -13 to confirm the subject is taking the right dose of medication. Nivolumab will be given after biopsy#2 (same day or up to 5 days later), and then repeated every 4 weeks.
- d. ECOG performance status should be done within 14 days or less from day 1 of cycle 1
- e. Lab results from screening may be used if completed within 1 week of day -1
- f. Baseline imaging within 4 weeks of day 1 is acceptable
- g. Scans will be done at the end of cycle 2 (± 3 days), then repeated every 2 cycles (q 8 weeks)

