8.1.7 Follow-up Visits

Subjects who discontinue trial treatment for a reason other than disease progression will move into the Follow-Up Phase and should be assessed every 8 weeks (\pm 7 days) by radiologic imaging to monitor disease status. After 1 year, the imaging time point will occur every 9 weeks (\pm 7 days). Every effort should be made to collect information regarding disease status until the start of new anti-neoplastic therapy, disease progression, death, end of the study or if the subject begins retreatment with nivolumab and metformin as detailed in Section 7.1.6.2. Information regarding post-study anti-neoplastic treatment will be collected if new treatment is initiated. Details are provided in Section 7.0 – Trial Flow Chart.

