10.2 Statistical and Analytical Plans

Summary statistics will be presented for all safety, efficacy and biomarker parameter analyses. The purpose of these analyses is hypothesis generating. Various exploratory statistical tests may be applied to data generated from this trial to generate hypotheses to be tested in subsequent trials. In general, data for continuous parameters will be presented using descriptive statistics including sample size, mean, and median; standard deviation; and minimum and maximum. Categorical parameters be displayed using counts and percentages. Toxicities will be presented as worst toxicity per patient and will be reported as percent toxicity.

Objective response rate will be calculated as proportion (Responders/Total patients) along with 95% confidence intervals using the Clopper-Pearson method. Chi-square test or Fisher's exact test will be used to compare the efficacy in term of response rate, biochemical response (CEA) between the different groups stratified by biomarkers or other factors, respectively. Logistics regression

model will be further employed to test the adjusted effect of biomarkers on the response rate after adjusting for other clinical factors and demographic factors.

For progression free survival, progression or death from any cause will be defined as the event. Patients will be censored at time of last follow-up. For overall survival, death from any cause will be defined as the event. Patients will be censored at time of last follow-up. Overall survival (OS) and progression free survival (PFS) rates of two patient groups stratified by response or other factors will be estimated with the Kaplan-Meier method and compared between different groups using the log-rank test, respectively. The PFS and OS of each patient group at specific time points, such as 6 months, 1 year, 3 year, and 5 year, etc. will be also estimated alone with 95% CI. Cox proportional hazards models will be further used in the multivariable analyses to assess adjusted effect of response on the patients' OS and PFS after adjusting for other factors. Interaction terms between these factors will also be tested for statistical significance. The proportional hazards assumption will be evaluated graphically and analytically with regression diagnostics. Violations of the proportional hazards assumptions will be addressed by use of time-dependent covariates or extended Cox regression models.

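### The study calendar and section 8.1.7 give incompatible rules for tumour imaging after treatment stops, and the PFS censoring date in 10.2 is too loose to absorb the difference

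*Combined protocol and SAP*

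**What the plan says.** **Study calendar (section 7).** The post-treatment Follow Up Visits column is headed "Every 8 weeks post discon" and carries footnote b: "Only for patients with ongoing treatment related toxicities". The Tumor Imaging row has marks at screening and during treatment only. Footnote g ties the scans to treatment cycles: "Scans will be done at the end of cycle 2", then every two cycles.

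**Section 8.1.7.** "Subjects who discontinue trial treatment for a reason other than disease progression will move into the Follow-Up Phase and should be assessed every 8 weeks" by imaging, moving to every 9 weeks after one year. This continues until new anti-cancer therapy, progression, death, end of study or retreatment.

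**Which governs.** Section 6.9 says: "Patients will be followed as outlined in study calendar in section 7 after removal from study or until death". Section 8.1.5 sends the reader to the flow chart for visit requirements, and 8.1.7 closes by doing the same.

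**PFS (10.2).** The event is progression or death from any cause. Otherwise: "Patients will be censored at time of last follow-up". That date is not defined further.

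**The concern.** Take a patient who stops by choice, or whose toxicity has resolved, with no progression. Section 8.1.7 requires continued scans. Under footnote b the patient has no 8-weekly visit, and no scan is marked in any case. Site staff who schedule from the calendar would omit scans that 8.1.7 requires.

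PFS is a stated secondary endpoint, and 10.2 names 6-month and 1-year estimates. A patient who is no longer scanned can have an event only by dying. If the censoring date may be a contact without imaging, the patient counts as progression-free over a period in which nobody looked for progression.

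**Working it through.** **1. The passages side by side**

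| Question | Calendar | Section 8.1.7 |
|---|---|---|
| Who is followed every 8 weeks after stopping? | Patients with ongoing treatment-related toxicity | All who stop for a reason other than progression |
| Is imaging scheduled after stopping? | None marked | Yes |
| Interval | 8 weeks (visits) | 8 weeks, then 9 weeks after year 1 |

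Passages that fit 8.1.7:
- Section 8.1.4 sends patients who stop after CR into the follow-up period of 8.1.7.
- Section 8.1.7.2 makes retreatment depend on radiographic progression seen after stopping.
- The synopsis gives scans every 8 weeks for 2 years and does not limit them to time on treatment.

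Passages that point to the calendar: 6.9, 8.1.5 and the last line of 8.1.7.

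**2. What the plan's own figures cover**

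The plan states no PFS, OS or discontinuation rate, so there is no PFS figure to reproduce. Its one design calculation is for ORR: at least 1 response in 18 to continue, at least 3 of 28 for success. At a 15% response rate the exact power of that rule is 0.803, matching the stated 80%. Off-treatment scanning is not an input to it.

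**3. Illustration for PFS (all inputs assumed)**

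- PFS is exponential with median 3 months: λ = ln2/3.
- Death follows progression by an exponential time with median 6 months: μ = ln2/6.
- A share f = 10% or 20% of those event-free at 2 months stop and are not scanned again.

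True PFS: S(6) = 2^(−6/3) = 25.0%; S(12) = 2^(−12/3) = 6.25%. Event-free at 2 months: 2^(−2/3) = 0.630.

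The probability that an unscanned patient is still alive u months after stopping is

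A(u) = [λ·exp(−μu) − μ·exp(−λu)] / (λ − μ).

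Since λ = 2μ, this is 2·2^(−u/6) − 2^(−u/3). So A(4) = 0.863, A(10) = 0.531 and A(1) = 0.988.

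*Case A: unscanned patients stay at risk and only death counts.* Apparent PFS at t is (1 − f)·S(t) + f·0.630·A(t − 2).

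| | f = 10% | f = 20% | True |
|---|---|---|---|
| 6 months | 0.90×0.25 + 0.10×0.630×0.863 = 27.9% | 0.80×0.25 + 0.20×0.630×0.863 = 30.9% | 25.0% |
| 12 months | 0.90×0.0625 + 0.10×0.630×0.531 = 9.0% | 0.80×0.0625 + 0.20×0.630×0.531 = 11.7% | 6.25% |

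The rise is 2.9 to 5.9 points at 6 months and 2.7 to 5.4 points at 12 months.

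*Case B: the same patients are censored at month 3, about the 30-day safety visit.* Kaplan-Meier at 3 months is 0.630×[(1 − f)×0.794 + f×0.988] = 0.512 or 0.524, against a true 0.500. Thereafter only scanned patients contribute. Multiplying by 2^(−1) gives 25.6-26.2% at 6 months. Multiplying by 2^(−3) gives 6.4-6.6% at 12 months. The shift is at most 1.2 points.

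**4. Wider range**

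A simulation used 8-weekly scans, median time to progression 2 or 4 months, median survival after progression 4 or 8 months, and 10-30% stopping before progression.

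- Unscanned, deaths counted, follow-up otherwise continued: PFS rises by about 2 to 15 points at both 6 and 12 months. The median rises by at most about 0.4 months.
- Censored 30 days after stopping: 6-month PFS changes by about 0 to +0.4 points.
- Censored at the last scan, with no scans after stopping: 6-month PFS falls by about 0.6 to 3 points.

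**5. Scale in this trial**

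0.630×28 = 17.6 patients are event-free at 2 months, and 10-20% of them is about 2 to 4 patients. For comparison, the exact 95% interval for 7 of 28 (25%) is 11% to 45%.

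**The case against.** The best defence is that the intent to scan is clear. Section 8.1 says the flow chart summarises procedures that are detailed below it, and 8.1.4, 8.1.7.2 and the synopsis all presuppose scans after stopping. Section 6.9 is not a precedence clause. This makes 8.1.7 a plausible reading of intent. It does not settle the matter, because footnote b is an explicit restriction rather than an omission from a summary, and three sections send the reader to the calendar. The extracted calendar has misaligned headers, so the empty imaging cells are weaker evidence. Footnote b carries the point without them.

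A reader might infer more than the documents support:

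- *That following the calendar necessarily inflates PFS.* Section 8.1.7.1 starts the 12-weekly telephone calls only after confirmed progression or new anti-cancer therapy. A patient who simply stops is not placed in those calls. Because last follow-up is undefined, the effect could be upward, negligible or, with censoring at the last scan, slightly downward.
- *That patients who stop after CR are never scanned again.* Section 8.1.4 sends them to 8.1.7, so this inference needs the reader to ignore that text.
- *That the primary result is compromised.* A first response after stopping could be missed, but that would lower ORR, not raise it. The decision rule is unchanged. Section 6.12 also treats some early stoppers as inevaluable for the primary endpoint and replaces them.
- *That 8 versus 9 weeks is certainly a contradiction.* The synopsis lists its scans under treatment, whereas the 9-week interval applies off treatment. The synopsis limit of 2 years leaves the overlap unclear, so it belongs in the reconciliation.

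It is also fair that PFS is secondary, has no threshold, and falls under analyses that 10.2 calls hypothesis-generating.

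**Conclusion.** The conflict stands, in current text. For patients who stop without progression and without ongoing toxicity, the calendar and 8.1.7 cannot both be followed. The consequence for PFS is possible rather than certain. The bias is upward, by about 3 to 6 points at 6 and 12 months in the illustration, only if unscanned patients stay at risk through later non-imaging contacts or until death. It is near zero if they are censored at about the 30-day visit. The size rests on assumed PFS, survival and discontinuation rates, since the plan gives none, and landmark rates move more than the median. The point should be corrected because the text leaves progression unobserved for a stated endpoint and leaves the censoring date open.

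**What to change.** 1. Reconcile footnote b and the Tumor Imaging row with 8.1.7, 6.9 and the synopsis, including the 8- versus 9-week interval, so that a single off-treatment imaging schedule applies and every section states it the same way. The choice of schedule is for the sponsor and the investigator.
2. In 10.2, censor patients without a PFS event at their last adequate tumour assessment, and keep last contact as the censoring date for OS only.

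Both parts are needed. With no scans after stopping, the censoring change alone removes the upward bias but loses follow-up, with the fall of 0.6 to 3 points shown above. The cost is text correction and slightly earlier PFS censoring for some patients. Section 8.1.7 as written already requires off-treatment scans.

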1. STUDY SYNOPSIS

| |
|---|
| 
Title of Study: Phase II trial of Nivolumab and Metformin in patients with treatment refractory MSS metastatic Colorectal Cancer
 |
| 
Study Centers: Emory University Winship Cancer Institute
 |
| 
Study Phase: Phase II
 |
| 
Objectives:
 
Primary Objective:
 
▪ The primary endpoint of this study is to Evaluate the effect of metformin in combination with nivolumab on the overall response rate (ORR) (Primary Objective) as assessed by RECIST.1.1 
Secondary Objectives:
 
▪ To determine the effect of the metformin and nivolumab combination on clinical (PFS, OS) outcomes and biochemical (CEA) response.▪ To compare the effect metformin and nivolumab combination on immune and metabolic biomarkers in the tumor microenvironment and systemic circulation (pre and post treatment paired biopsies required). |
| 
Trial Design/Methodology: Single arm phase II study. 28 patients with previously treated (previously treated with fluoropyrimidine, oxaliplatin, irinotecan and EGFR inhibitor – if RAS wildtype) metastatic CRC will be started on metformin and nivolumab combination.
 
Treatment
 
1. Patients will start taking metformin 500 mg po BID for 3 days, then 500 mg am and 1000 mg pm for 4 days, then 1000 mg po bid for 1 week. Patients of the study will get paired biopsies as outlined in study calendar.2. If a patient cannot tolerate metformin 1000 mg po BID the patient will resume the metformin dose which was tolerable3. After 2 weeks of metformin only therapy (lead-in period) patients will start nivolumab 480 mg IV q4 weeks and continue metformin 1000 mg PO BID (or the tolerated dose of Metformin).4. Restaging scans will be performed at the end of cycle 2, then every 8 weeks for 2 years.5. Correlative assays will include- immune profiling of TILs and circulating lymphocytes, plasma cytokine levels and metabolic biomarkers. These will be performed at baseline at baseline, cycle 1 day 1, cycle 1 day 15, Cycle 3 Day 1 and at progression 
Treatment regimen and trial diagram:
 |

Main criteria for exclusion:

- MSI status
- Autoimmune conditions that may require systemic steroids or other immunosuppressive treatments
- Pregnancy or breast feeding

Investigational product and administration:

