7. STUDY CALENDAR

Winship Protocol #: Winship4494-18
Protocol: Nivolumab + Metformin
Protocol/Amendment No.: Version 6/June 13, 2023
Study Flow Chart

36

| Trial Period: | | Treatment Cycles ^a | | | | | | | | | | End of Treatment | Post-Treatment | | |
|---|----------------|--------------------------------|-----|----------------|------|-----|-----|-----|-----|-----|-----|-------------------|---------------------|-------------------------------|--------------------|
| | | Main Study Screening (Visit 2) | | 1 ^a | 2 | 3 | 4 | 5 | 6 | 7 | 8 | | | | |
| Treatment Cycle/Title: | Day | D-14 | D-7 | D1 | D15 | | | | | | | Discon | Safety Follow-up | Follow Up Visits ^b | Survival Follow-Up |
| Scheduling Window (Days): | -28 to -1 | | | ± 3 | ± 3* | ± 3 | ± 3 | ± 3 | ± 3 | ± 3 | ± 3 | At time of Discon | 30 days post discon | Every 8 weeks post discon | Every 12 weeks |
| Informed Consent | X | | | | | | | | | | | | | | |
| Inclusion/Exclusion Criteria | X | | | | | | | | | | | | | | |
| Demographics and Medical History | X | | | | | | | | | | | | | | |
| Prior and Concomitant Medication Review | X | X | X | X | X | X | X | X | X | X | X | X | X | X | |
| Metformin Administration ^c | | X | X | X | X | X | X | X | X | X | X | | | | |
| Drug Diary and Pill Count (Metformin) section 13.5 ^c | | X | | X | X | X | X | X | X | X | X | X | | | |
| Blood glucose log for diabetic patients | | X | X | X | X | | | | | | | | | | |
| Nivolumab administration ^c | | | | X | | X | X | X | X | X | X | | | | |
| Post-study anticancer therapy status | | | | | | | | | | | | | X | X | |
| Survival Status | | | | | | | | | | | | | X | X | X |
| Review Adverse Events | | | X | X | X | X | X | X | X | X | X | X | X | X | |
| Full Physical Examination | X | X | | X | | X | X | X | X | X | X | | | | |
| Directed Physical Examination | | | | | X | | | | | | | | X | X | X |
| Vital Signs and Weight | X | X | | X | X | X | X | X | X | X | X | X | X | X | |
| ECOG Performance Status ^d | X ^d | X | | X | X | X | X | X | X | X | X | X | X | X | |
| Pregnancy Test – Urine or Serum β-HCG | X ^j | | | | | | | | | | | | | | |
| PT/INR and aPTT | X | | | | | | | | | | | | | | |
| CBC with Differential | X | X ^e | | X | X | X | X | X | X | X | X | X | X | X | |
| Comprehensive Serum Chemistry Panel | X | X ^e | | X | X | X | X | X | X | X | X | X | X | X | |
| Fasting triglyceride, cholesterol and glucose | X | | | | | X | | | X | | | | | | |
| CEA | | X | | X | X | | X | | X | | X | | | | |

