- h. Paired biopsies (biopsy#1) will be obtained at baseline from all 28 patients within 28 days before Cycle 1 day 1 after consent is signed, subject #1-9, 19-23 (14 patients in total) will get post treatment biopsy (biopsy#2) cycle 1 Day 1 (same day or up to 5 days later) nivolumab will be given after biopsy#2 (same day or up to 5 days later) and subject# 10-18, 24-28 (14 patients in total) will get post treatment biopsy (biopsy#2) C1 Day 15 (same day or up to 5 days later). Most accessible metastatic disease tumor site will be biopsied by Emory Interventional Radiology. Same site will be biopsied at biopsy#1 and biopsy#2. 3 core biopsies will be obtained each time. If a patient undergoes biopsy#1 and refuse biopsy#2 this subject will be replaced. Subjects continue metformin on days of biopsy#2, and take metformin preferably 2 hours prior to the biopsy.

- i. Correlative samples will be collected at baseline, cycle 1 day 1, cycle 1 day 15, Cycle 3 Day 1 and at progression. Analysis will include phenotypic and functional analysis of T and myeloid cell subsets.

- j. Must be within 72 hours of the study drug

*Unless otherwise specified

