8.1.5.4 Cycle 1 Day -7 phone call

- Metformin
- Review of adverse events, dosing compliance and concomitant medication (by clinical trial coordinator via phone call)

8.1.5.5 Cycle 1 Day 1

- Record concomitant medications
- Vitals (temperature, HR, BP and RR)
- History and physical exam, pill diary and pill count, blood glucose log for diabetic patients
- ECOG performance status
- Toxicity assessment
- Laboratory Assessments
 - Hematology hemoglobin, hematocrit, red blood cell count, white blood cell count with differential and platelet count
 - Chemistry sodium, potassium, chloride, bicarbonate, magnesium, calcium, phosphorus, blood urea nitrogen, creatinine, glucose (random), total bilirubin, LDH, total protein, ALP, ALT, AST, and albumin
- Blood sample 20 cc for correlative work
- **Subject# 1-9, 19-23** (14 patients in total) will get biopsy#2 of paired biopsy (same day or up to 5 days later)
- Continue metformin
- Nivolumab will be started after biopsy#2 (same day or up to 5 days later).
- Nivolumab 480 mg will be administered as a 30-minute IV infusion in the infusion center. Given the variability of infusion pumps, a window of -5 minutes and +10 minutes is permitted (i.e., infusion time is 30 minutes: -5 min/+10 min).

8.1.5.6 Cycle 1 Day 15

- Record concomitant medications
- Vitals (temperature, HR, BP and RR)
- History and physical exam, pill diary and pill count, blood glucose log for diabetic patients
- ECOG performance status

- Toxicity assessment
- Laboratory Assessments
 - Hematology hemoglobin, hematocrit, red blood cell count, white blood cell count with differential and platelet count
 - Chemistry sodium, potassium, chloride, bicarbonate, magnesium, calcium, phosphorus, blood urea nitrogen, creatinine, glucose (random), total bilirubin, LDH, total protein, ALP, ALT, AST, and albumin
 - Tumor marker – CEA
- Blood sample 20 cc for correlative work
- The second half of the patients **Subject #10-18, 24-28** (14 patients in total) will get biopsy#2 of paired biopsy (same day or up to 5 days later)
- Continue metformin

8.1.5.7 Cycle 2 Day 1

- Record concomitant medications
- Vitals (temperature, HR, BP and RR)
- History and physical exam, pill diary and pill count
- ECOG performance status
- Toxicity assessment
- Laboratory Assessments
 - Hematology hemoglobin, hematocrit, red blood cell count, white blood cell count with differential and platelet count

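### First nivolumab is tied to biopsy #2 with no subject group named; for the 14 subjects biopsied at C1D15 the passages conflict, and so does the exposure their tissue represents

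*Combined protocol and SAP*

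**What the plan says.** Two passages give the rule without limiting it to a group:

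- Section 7, footnote c, referenced from the nivolumab row of the calendar: "Nivolumab will be given after biopsy#2 (same day or up to 5 days later), and then repeated every 4 weeks".
- Section 8.1.5.5 (Cycle 1 Day 1): "Nivolumab will be started after biopsy#2 (same day or up to 5 days later". A nearby bullet limits the Day 1 biopsy to subjects 1-9 and 19-23; the nivolumab bullet carries no such limit.

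Other passages bear on the same dose:

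- Section 7, footnote h, for subjects 1-9 and 19-23: "will get post treatment biopsy (biopsy#2) cycle 1 Day 1 (same day or up to 5 days later) nivolumab will be given after biopsy#2". For the rest: "subject# 10-18, 24-28 (14 patients in total) will get post treatment biopsy (biopsy#2) C1 Day 15 (same day or up to 5 days later", with no nivolumab clause. Section 8.1.3.1 repeats the biopsy schedule and is silent on nivolumab.
- Synopsis, treatment item 3: "After 2 weeks of metformin only therapy (lead-in period) patients will start nivolumab 480 mg IV q4 weeks and continue metformin". No group is named.
- The calendar grid has one nivolumab row for all subjects, marked at C1D1 and blank at C1D15.
- Section 8.1.5.6 (Cycle 1 Day 15) lists the second group's biopsy and continued metformin, but no nivolumab.
- Section 6.1.1, Table 1, covers cycle 1 from Day -14 through Day 28 and lists only metformin. Nivolumab first appears in Table 2, for cycle 2 onward.

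Secondary objective 2 (section 3.2) concerns the effect of the combination on biomarkers in the tumor microenvironment and in the circulation, and requires paired biopsies.

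**The concern.** Splitting the second biopsy between C1D1 and C1D15 appears to serve a purpose: tissue after metformin alone from one half, and tissue after both drugs from the other. That holds only if the C1D15 group has received nivolumab before its biopsy. Footnote c and the Day 1 bullet, applied to this group, reverse the order. For these 14 subjects a coordinator cannot follow both footnote c and the synopsis and grid, and the calendar's nivolumab row sends the reader to footnote c.

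At stake is whether the trial yields any tissue taken on the combination, and whether the C1D15 blood sample represents one exposure or two. Section 10.2 gives no rule for assigning a biopsy to metformin alone or to the combination, so the analysis would not reveal the difference.

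**Working it through.** **Group sizes (footnote h).** Subjects 1-9 and 19-23: 9 + 5 = 14. Subjects 10-18 and 24-28: 9 + 5 = 14. Together they cover 1 to 28 once each, which reproduces the plan's 14 per group. Stage 1 is the first 18 patients (section 10.1); subjects 10-18 are 9 of them.

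**First nivolumab under footnote c.** Biopsy day = nominal day + 0 to 5; nivolumab day = biopsy day + 0 to 5.

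- C1D1 group: biopsy D1 to D6; nivolumab D1 to 6 + 5 = D11.
- C1D15 group: biopsy D15 to D20; nivolumab D15 to 20 + 5 = D25. Adding the calendar's ±3-day window gives D12 to D28.
- Metformin-only time in the C1D15 group, with a 14-day lead-in and no Day 0: 14 + 14 = 28 to 14 + 24 = 38 days. The synopsis gives 14.

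**What each sample represents.** Assumptions: C3D1 is D57 (two 28-day cycles counted from D1), and C1D15 blood is drawn before any same-day infusion. In the second column the C1D15 group receives nivolumab on nominal D1.

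| | Footnote c for all | Footnote h with the grid |
|---|---|---|
| Biopsy #2, C1D1 group (14) | metformin alone | metformin alone |
| Biopsy #2, C1D15 group (14) | metformin alone | combination, 15 - 1 = 14 to 20 - 1 = 19 days after first nivolumab |
| Biopsies on the combination | 0 of 28 | 14 of 28 |
| C1D15 blood, C1D1 group | combination, 15 - 11 = 4 to 15 - 1 = 14 days | the same |
| C1D15 blood, C1D15 group | metformin alone | combination, 14 days |
| C3D1 blood, C1D15 group | combination, 57 - 25 = 32 to 57 - 15 = 42 days | combination, 56 days |

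The literal reading therefore also splits the C1D15 blood sample into two exposures, even if every patient is handled identically.

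**Tables 1 and 2 as they read.** First nivolumab would fall on Day 1 of cycle 2, that is D29. Every second biopsy is due by D20, so this reading too gives 0 of 28.

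**Exposure before the first scan.** The end of cycle 2 is D56. From first nivolumab to scan: 56 - 1 = 55 days for a D1 start; 56 - 15 = 41 down to 56 - 25 = 31 days for a D15 to D25 start. With repeats every 4 weeks, dose 2 falls on 15 + 28 = D43 to 25 + 28 = D53, against D29 for a D1 start. Both schedules give two doses before D56.

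**The case against.** The best reply is that the documents, taken together, do not schedule nivolumab on Day 15 to Day 25. Footnote h, the dedicated biopsy footnote, attaches the clause only to the C1D1-biopsy group. The section 8.1.5.5 bullet sits in a Day 1 list, shortly after a biopsy bullet limited to that group. The synopsis, the grid and the C1D15 list all point to Day 1. This stands: the defect is an unscoped sentence that other passages contradict. But footnote h never says when the other group starts nivolumab, and Table 1 leaves nivolumab out of cycle 1 altogether, so the text does not settle itself.

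Three stronger readings are tempting and are not supported:

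- **Response rate and the stage 1 decision are compromised.** Time to the first scan would be shorter, but two doses still precede it, and the C1D1 group may itself start as late as D11, which is 56 - 11 = 45 days before the scan. Scans continue every 8 weeks, sections 10.1 and 10.2 do not tie ORR to the first scan, and no figure in the documents links such a delay to response.
- **Secondary objective 2 becomes unanswerable.** It also covers the circulation. C3D1 blood is on the combination under either column of the table, and a progression sample is also planned. Section 10.2 describes these analyses as hypothesis generating.
- **Sites will differ.** The synopsis names one centre, and section 11.5 describes weekly team review of each patient. Inconsistency between patients remains possible; inconsistency between sites does not arise.

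**Conclusion.** The contradiction is real and limited in scope. For 14 of 28 subjects the protocol gives incompatible timings for first nivolumab: D15 to D25 under footnote c and the Day 1 bullet, Day 1 under the synopsis and grid, and no cycle 1 dose in Table 1. The number of second biopsies taken on the combination is 0 or 14 of 28 accordingly. What depends on it is the tissue part of secondary objective 2 and the interpretation of C1D15 blood. C3D1 and progression blood are less affected, and no effect on the primary endpoint is shown.

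The counts assume that subjects follow the numbering in footnote h and that study days run from C1D1. The documents do not show which passage was followed in practice, so how many biopsies are affected is unknown. The point merits correction because a written rule, followed as it stands, would remove all on-combination tissue from an objective that requires paired biopsies.

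**What to change.** Reconcile the synopsis, Tables 1 and 2 in section 6.1.1, the calendar grid, footnotes c and h, and sections 8.1.5.5 and 8.1.5.6, so that first-nivolumab timing is stated once and consistently for each biopsy group. Section 8.1.3.1 should refer to the same statement. The sponsor decides the schedule; this review does not choose between the passages.

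In section 10.2, define an exposure class for each biopsy #2 and each C1D15 blood sample, metformin alone or combination, from the recorded nivolumab and sample dates and not from subject number. Where sample and infusion fall on the same day, use their recorded order. Report the number in each class and the days since first nivolumab. If the combination class for tissue is empty, describe the tissue results as the effect of metformin alone.

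The cost is a protocol clarification and one derived variable. No visit, biopsy or blood draw is added.
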